**Date of protocol: 20/01/2022**

## **Background**

Breast milk composition is believed to be highly variable due to an extensive array of factors which include maternal diet. Many previous studies have provided insights into the potential role of maternal dietary intake on the concentrations of key macronutrient (fat, protein and lactose) in human milk. These studies have suggested that concentrations of lactose, the most abundant carbohydrate (Smilowitz et al. 2013), are not affected by the maternal diet (Smilowitz et al. 2013 and Nommsen et al. 1991). Similarly, total protein concentrations in human milk are thought to be relatively stable, with some evidence even showing a compensatory ability for women to maintain consistent protein concentrations in their milk despite consuming diets low in protein (Lonnerdal 1986). Fats are known to be the most variable macronutrient in human milk, with many studies demonstrating that both the fat content and fatty acid composition of human milk shifts rapidly in response to changes in these factors in the maternal diet (Mohammed et al. 2009 and Henjum et al. 2018). However, there are significant weaknesses in the existing literature base, since the majority of these studies have measured effects on human milk composition in pooled samples collected over a 24-hour period before analysis. This means that they have no capacity to consider how milk composition varies over a day, or the effects of dietary changes on human milk composition in the short-term.

The design of the proposed research is based upon our recently published UK pilot study where 9 women were each given a control/higher sugar/higher fat diet over 3 separate days (Ward et al. 2021). On each of the 3 days breast milk was collected hourly for a period of 12 hours. The study showed a significant increase in breast milk triglyceride concentrations following a higher sugar diet, compared to a control diet ( $p < 0.001$ ). It was also identified that statistically significant variations in breast milk protein and lactose concentrations occurred across the 12-hour sampling period, indicative of a circadian rhythm that had not been previously reported. Given the novelty of the study protocol, and the study findings, it is important to confirm these in a larger group of women.

The aim of this study is to explore in greater detail the impact of sugar on breast milk triglycerides and the changes in milk protein and lactose across the course of a day. This research will provide a positive contribution to the current knowledge base as to the source of variations in breast milk composition and lead to better formed advice for breastfeeding mothers and health care professionals.

## **Aims**

1. To determine the effect of increased sugar consumption on the composition of breast milk.
2. To assess variations in breast milk composition across the day
3. To evaluate variations in breast milk composition across the different stages of lactation in general.

## **Study Design**

The study design follows that of a similar pilot study which was completed in 2019, (Ward et al., 2021). Exclusively breastfeeding mothers will be recruited using online platforms and will be provided with two separate diets across two full days (diets will either be control

(aligned with the Australian Guide to Healthy Eating) or contain a higher amount of sugar). Concurrently participants will be asked to collect hourly breast milk samples by manual expression. Breast milk samples will be analysed for compositional elements such as macronutrients to determine if increased sugar consumption influences breast milk composition.

### **Study Population**

40 mother/baby dyads in total; 20 with infants between 6-12 weeks and 20 with infants between 13-20 weeks at time of enrolment.

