### **Inclusion criteria**

#### Inclusion

- Healthy mothers of singleton infants born at full term (>38 weeks gestation)
- Mothers between the ages of 21-35 years
- Mother with a BMI between 20 and 30 kg/m^2
- Infants between 6 and 20 weeks of age at the time of recruitment
- Mother and infants have no self-reported underlying medical conditions/special dietary requirements which result in restriction of any major food groups (e.g. vegan/dairy allergy)
- Mother able to give informed consent for themselves and their infants
- Mothers have been exclusively breastfeeding their infant since birth (with the exception of additional water or medication such as paracetamol suspensions)

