### **Screening telephone call**

- A chance to ask questions and discuss any concerns about the study before signing informed consent form. A copy of the diets will be provided (appendix 3).
- A questionnaire regarding mother's health including height and weight information, infant's health and infant feeding patterns will be completed.
- Information regarding dietary data collection along with instructions on how to fill in the diet diaries will be provided (see appendix 2).
- Following confirmation of suitability mothers will be contacted and asked to complete the diet diary for 3 days prior to the home visit.

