## **Study Intervention**

The intervention within this study includes two different diets; one control and one higher in sugar. A cross-over design will be used where control and higher sugar diets will be provided in a random order to each woman across visit 2 and 3. Participants will be encouraged to try and avoid consuming foods other than those provided but can resume their normal eating habits once the last sample has been collected. If women consume anything other than the foods provided, they will be asked to record this information, similarly, if they do not consume all food provided they will be asked to retain the food for the student investigator to weigh and estimate the percentage of consumption at each meal.

There will be 7 days between these visits to allow for a washout period between diets.

There are no dietary restrictions during the washout period.

Participants will be discouraged from consuming caffeine or alcohol during the study period (i.e. days when intervention diets are being consumed).

The paired design means that in the analysis of the data each woman will act as her own control.

Considering dyads at two different infant ages will enable the project to address the third aim and determine whether milk composition varies across lactation and whether sensitivity to maternal diet may change over time.

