### **Statistical Analysis Plan**

Statistical analyses will be performed using SPSS software (version 21; IBM, Armonk, NY). Statistically significant differences in the variability of milk compositional concentrations will be determined using repeated and single measures ANOVA with Tukeys HSD post hoc tests where appropriate. A Bonferroni correction will be used to control for multiple comparisons. Statistical significance will be accepted with a *P* value of <0.05 and all results will be presented as mean with ± standard error of the mean.

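### Aim 3 rests on two adjoining infant-age bands although age is continuous over 6–20 weeks; using exact age would recover about a quarter of the age information if ages are evenly spread and the trend is roughly linear

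*Protocol*

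**What the plan says.** - **Aim.** The third aim (Protocol, Aims) is "To evaluate variations in breast milk composition across the different stages of lactation in general".
- **Eligibility.** The inclusion criteria admit "Infants between 6 and 20 weeks of age at the time of recruitment", with no gap in the range.
- **Groups.** Study Population sets two equal bands, "20 with infants between 6-12 weeks and 20 with infants between 13-20 weeks at time of enrolment".
- **Route to the aim.** Study Intervention states: "Considering dyads at two different infant ages will enable the project to address the third aim and determine whether milk composition varies across lactation". The same sentence adds the question whether sensitivity to maternal diet changes over time.
- **Method.** The section headed Statistical Analysis Plan names "repeated and single measures ANOVA with Tukeys HSD post hoc tests where appropriate". It does not say how infant age enters, and no section uses age as a continuous variable.
- **Power.** Statistical Power uses a paired-samples calculation for triglycerides (90% power, 1% significance). It arrives at 13 dyads per age band, raised to 20 for drop-out.
- **Timing.** After screening, "mothers will be contacted and asked to complete the diet diary for 3 days prior to the home visit". Between the two diet days, "There will be 7 days between these visits to allow for a washout period between diets". No maximum interval from enrolment to the first diet day is given.

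**The concern.** Each woman supplies milk on both diet days, so the diet effect is measured within women. Stage of lactation is measured between women, one infant age per dyad, and is therefore much less precise. Replacing a continuous age by a two-level label throws away the spread within each band. An infant of 6 weeks counts the same as one of 12, while infants of 12 and 13 weeks are treated as being at different stages.

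What is at stake is the power to see a trend in milk composition with age, and the width of the interval around it. The same applies to the diet-by-age interaction. The protocol promises an answer to both questions, but the sample size was not set for either.

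**Working it through.** **1. The plan's own figure.** The 13 per band cannot be reproduced directly, because neither the SD of the paired difference nor the reduced effect is stated. Solving backwards (two-sided 1%, 90% power, noncentral t), n = 13 corresponds to a paired effect of 1.25 SD; the normal approximation gives (2.576 + 1.282)/√13 = 1.07 SD. Going from 13 to 20 implies 35% drop-out: 13/(1 − 0.35) = 20. All of this concerns the within-woman diet contrast only.

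**2. Share of age information kept by the band label.** For a linear trend, this share is the squared correlation between age and band. With half the women in each band:

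share kept = B/(B + W), where B = (gap between band means / 2)² and W = the average of the two within-band variances (width²/12 for even spread).

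| Assumed ages | Gap (weeks) | B | W | Share kept |
|---|---|---|---|---|
| Even over 6–20, cut at 13 | 7.0 | 12.25 | 4.083 | 0.750 |
| Even over 6w0d–12w6d and 13w0d–20w6d | 7.5 | 14.063 | 4.708 | 0.749 |
| Same, in completed weeks | 7.5 | 14.063 | 4.625 | 0.753 |
| Bands read as 6.0–12.0 and 13.0–20.0 | 7.5 | 14.063 | 3.542 | 0.799 |

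Simulation under uneven ages gives 0.66 (bell-shaped around 13 weeks, SD 3), 0.71 (clustered near the cut) and 0.95 (clustered at the two ends). The loss is therefore about 25% for even ages, and about 5% to 34% over the distributions tried. The protocol gives no age distribution; all of these are assumptions.

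**3. What that costs.** 0.75 × 40 = 30 effective women. As an illustration, take a true correlation of 0.43 between age and a milk component, a two-sided 5% test, and power ≈ Φ(atanh(r)·√(n − 3) − 1.96):
- 40 women, exact age: 80%. Band label, with r = 0.43 × √0.75 = 0.372: 66%.
- 26 women (13 per band after drop-out): 60% against 47%.

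**4. Does the delay between enrolment and sampling matter?** The diary takes at least 3 days and the second diet day is 7 days after the first. Take enrolment as the point where the diary is requested, and enrolment ages as even over the 49 days of the younger band. Then 3/49 = 6% of that band have reached 13 weeks by the first diet day and 10/49 = 20% by the second. But the older band ages too. A common delay leaves the gap between band means at 7.5 weeks and the share kept at 0.75. With delays varying at random from 3 to 28 days the gap is still 7.5 weeks, and the share kept falls only to 0.71.

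**5. Is the comparison between bands powered?** The diet-by-band comparison is a two-sample comparison of paired differences. Suppose the effect is 1.25 SD in one band and half that in the other, a difference of 0.625 SD. The halving is an illustration, and the bands are assumed to have equal SDs. Power is then:

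| Women per band | Two-sided 1% | Two-sided 5% |
|---|---|---|
| 13 | 14% | 33% |
| 20 | 25% | 49% |

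**The case against.** **The analysis is not fixed, so nothing is discarded yet.** A recruitment quota loses no information. The Statistical Analysis Plan section is general, does not exclude a covariate, and the coding of age could be left to a separate plan that is not shown. This stands in part: the loss arises only if the analysis uses band alone. But the protocol itself says "Considering dyads at two different infant ages will enable the project to address the third aim" and names only ANOVA, so a banded comparison is the natural reading.

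**A reader might infer that infants are misclassified** because some in the younger band reach 13 weeks before giving milk. The documents do not support this. The bands are defined by age at enrolment, and by that definition every infant is in the right one. The crossing shares in step 4 show only that the band is an approximate label for age at sampling.

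**A reader might also infer that banding pulls the lactation or diet-by-age effect toward zero.** It does not. The contrast between bands estimates the difference between those bands without attenuation. The mean age gap is unchanged by a similar delay in both, and diet order is randomised, so ageing between visits is not tied systematically to diet. The harm is lost precision.

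**Statistical Power never claims to cover Aim 3.** That is correct. The low power in step 5 is no error in the calculation. It shows only that to say the study will *determine* these questions is stronger than its size supports.

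**Entering age separately at each visit would create a new problem.** This also stands. The visits are 7 days apart for everyone, so within-woman change in age is the same thing as the period effect.

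**Conclusion.** The point holds as one of efficiency for a stated aim. Comparing two adjoining bands loses about 25% of the age information if ages are evenly spread and the trend is roughly linear, and about 5% to 34% under the other age distributions tried. If the true change were a step at 13 weeks, banding would lose nothing. The loss falls on a between-women comparison outside the 90% power, 1% significance calculation, where precision is already limited. It does not bias the band contrast, and it leaves the within-woman diet comparison, which the sample size was set for, untouched.

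**What to change.** - **Design.** Keep the two bands as recruitment quotas.
- **Statistical Analysis Plan.** State that Aim 3 is analysed with exact infant age as a continuous between-woman covariate, one value per woman (for example age at Visit 2, or the mean over the two sampling days). Add a diet-by-age term, model period separately, and report the slope and interaction with 95% confidence intervals.
- **Study Intervention.** Replace *determine* with *estimate*, and note there or under Statistical Power that the 90% power, 1% significance figure applies only to the within-woman diet contrast.

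The cost is wording. No further women, samples or visits are needed. The protocol does not list date of birth among the items recorded, but infant age has to be established to confirm eligibility and assign the band, so it should be recorded to the day.

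The downside is that a linear term assumes an approximately straight trend over 6–20 weeks. Check it with a plot or a quadratic term. The two-band comparison can stay as a descriptive summary.

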### **Recruitment**

Advertisements for the study will be posted on social media websites such as Facebook and will also be shared by associations for breastfeeding mothers such as Australian Breastfeeding Association. These advertisements will include contact details for the primary researcher to allow prospective participants to express interest. Following expression of interest potential participants will receive information on the study design and eligibility criteria. If they are still interested and deem themselves eligible then a screening telephone call will be arranged. Planned recruitment will commence in March 2022 and will continue until we have obtained the required number of participants.

### **Inclusion criteria**

#### Inclusion

- Healthy mothers of singleton infants born at full term (>38 weeks gestation)
- Mothers between the ages of 21-35 years
- Mother with a BMI between 20 and 30 kg/m^2
- Infants between 6 and 20 weeks of age at the time of recruitment
- Mother and infants have no self-reported underlying medical conditions/special dietary requirements which result in restriction of any major food groups (e.g. vegan/dairy allergy)
- Mother able to give informed consent for themselves and their infants
- Mothers have been exclusively breastfeeding their infant since birth (with the exception of additional water or medication such as paracetamol suspensions)

#### Exclusion

- Infants who were born by caesarean section
- Infants who are fed formula milk or fed a mixture of breast milk and formula
- Mothers who are struggling with breast feeding and/or are unable to manually express milk.
- Mother and/or baby who has an allergy/intolerance/aversion to the study diet (e.g. lactose intolerance).

### **Informed Consent**

Participants will provide a freely given verbal consent to undergo trial-related phone screening. The Principal Investigator or designee will ensure that all participants must provide written informed consent before undergoing any in-person screening activity or study procedure. Participants will have the opportunity to discuss their involvement with a friend or family member, and to ask study staff any questions they have about the study and have these answered to their satisfaction prior to providing informed consent. Participants

will be given a copy of the signed informed consent forms, whilst original copies will be kept by the researcher.

### **Withdrawals**

Consent is entirely optional and can be withdrawn at any time throughout the study without the need to provide reasons. Participants will be notified of their ability to withdraw at any time within the participant information sheet and will be reminded verbally during the screening visit.

Any data collected before the point of expressing desire to withdrawal will be retained along with the rest of the study data.

The PI or designee may also withdraw a participant from the study at any time. In this event, the clinic will ensure the reasons have been clearly explained to the individual.

## **Study Visits and Procedures**

The study design follows that of a similar pilot study which was completed in 2019, (Ward et al., 2021).

### **Screening telephone call**

- A chance to ask questions and discuss any concerns about the study before signing informed consent form. A copy of the diets will be provided (appendix 3).
- A questionnaire regarding mother's health including height and weight information, infant's health and infant feeding patterns will be completed.
- Information regarding dietary data collection along with instructions on how to fill in the diet diaries will be provided (see appendix 2).
- Following confirmation of suitability mothers will be contacted and asked to complete the diet diary for 3 days prior to the home visit.

### **Visit 2&3/Intervention (within participants' home)**

- Three main meals as well as snacks will be provided following specific diets (standardised/higher sugar). The meals may be tailored to personal preferences to a certain degree (allowing for all major food groups to remain included). Consumption at each meal will be measured by weighing anything not consumed at the end of the study day.
- Breakfast will be eaten when participants wake up, this will start the sample collection period. Lunch and dinner will be consumed at 5 and 10 hours from breakfast respectively. Snacks can be consumed at any time between meals and will be logged on a written document alongside fluid intake over the day.
- A 5-10mL sample of fore milk will be collected into a 10 mL polyprop vial and will be obtained by the mother by manual expression at hourly intervals in privacy within participants' homes.
- Women will be asked to record infant feeding times and duration.
- Record any adverse events, concomitant medication changes
- Babies will be weighed by the student investigator (or in the case of the Covid-19 safe protocol, scales will be provided for mothers to weigh their babies).

## **Covid-19 Safe Protocols**

In the case of increased requirements for Covid-19 safety the below protocols will be adhered to. These are designed to limit contact and prevent entrance of the student investigator into participants' homes in order to protect both parties.

- Face masks and gloves will be worn at all times during food preparation.
- Each participants' meals and sample collection materials (including relevant paperwork and instructions) will be placed in separate boxes/carrier bags for transportation. Meals will be transported from CSIRO to participant homes in a crate which has been cleaned with alcohol wipes.
- During deliveries/collections a mask will be worn and hands will be sanitised before any handling of study materials. Unless exempt, the research participant will be asked in advance to wear a face mask during drop-off.
- Deliveries will be placed at the doorstep/agreed location, researcher will step back and wait until it has been collected by the participant. A minimum distance of 2 metres will be kept from one another at all times. The researcher will not enter the residence of research participants and drop offs/collections will always take place outside of the building or property.
- Collection of study materials and samples will occur in the same way; participants will place the collection on the doorstep/agreed location and step back until it has been collected. The student investigator will transport collected items in a crate to CSIRO and will clean sample tubes with alcohol wipes before proceeding. Any other items such as transportation crates/boxes will be cleaned.

## **Study Intervention**

The intervention within this study includes two different diets; one control and one higher in sugar. A cross-over design will be used where control and higher sugar diets will be provided in a random order to each woman across visit 2 and 3. Participants will be encouraged to try and avoid consuming foods other than those provided but can resume their normal eating habits once the last sample has been collected. If women consume anything other than the foods provided, they will be asked to record this information, similarly, if they do not consume all food provided they will be asked to retain the food for the student investigator to weigh and estimate the percentage of consumption at each meal.

There will be 7 days between these visits to allow for a washout period between diets.

There are no dietary restrictions during the washout period.

Participants will be discouraged from consuming caffeine or alcohol during the study period (i.e. days when intervention diets are being consumed).

The paired design means that in the analysis of the data each woman will act as her own control.

Considering dyads at two different infant ages will enable the project to address the third aim and determine whether milk composition varies across lactation and whether sensitivity to maternal diet may change over time.

## **Diets**

Both diets will consist of ~2500 kilocalories over the course of the day and have been designed with the help of a registered dietitian at University of Nottingham. We aim to

provide a healthy balanced diet meeting as many of the recommended daily intakes for lactating women as possible. The designed diets for this study are the same (allowing for differences in brands/products available) as those provided during the UK pilot study. The higher sugar diet will be similar to the control, however, sugar content will be higher across the day amounting to an extra ~65g. E.g. high sugar cereals instead of low sugar cereals, jam added to toast. An itemised breakdown of both diets is included in the supplementary material.

Meals may be variable between participants as there will be the opportunity for some personalisation to accommodate preferences or any dietary constraints (e.g. vegetarian). Women will be asked to record fluid intake during the study.

